## 1. Abstract (Brief Summary)

This is a national, multicenter, retrospective cohort study based on real-world data from approximately 3,500 patients with breast phyllodes tumor (PT) diagnosed between 2001 and 2023 across 8 tertiary hospitals in China. The study aims to systematically describe the clinicopathological characteristics, treatment patterns, and long-term prognosis of Chinese PT patients. The primary outcomes are local recurrence (LR), distant metastasis (DM), and overall survival (OS). Secondary outcomes include disease characteristics and current treatment practices. This study will provide Chinese population evidence to support personalized treatment and guideline updates.

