#### **2.2.5 Gaps in Current Research – Domestic and International**

Domestic research on PT started relatively late. Xu et al. (2022) noted that Chinese studies have focused on clinical presentation, pathological diagnosis, and surgical treatment, but sample sizes are generally small, making multivariable adjustment difficult [25]. Most published studies are single-center retrospective analyses of dozens to a few hundred cases, lacking large-scale, national multicenter studies. The largest Asian retrospective study to date, from the electronic database of the First Affiliated Hospital of Xi'an Jiaotong University (Li et al., 2025) [24], is a dual-center study of 829 cases, but due to the rarity of the disease and limited geographic representation, it still cannot fully capture the characteristics of the entire Chinese population.

Although international studies have relatively larger sample sizes, they are mostly based on Western populations, and Chinese patient data are lacking. Moreover, most are single-center retrospective analyses, and sample sizes are still insufficient for adequate subgroup analyses. Currently, there are few systematic studies on recurrence patterns (time to recurrence, number of recurrences, grade progression after recurrence), and the dynamic pattern of PT progression remains to be further elucidated.

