### **3. Study Objectives and Endpoints**

#### **3.1 Objectives**

##### **3.1.1 Primary Objective**

To systematically elucidate the survival and prognostic characteristics of Chinese patients with breast phyllodes tumor (PT) using 20-year real-world data from a national multicenter cohort.

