##### **3.1.2 Secondary Objectives**

(1) Describe distribution characteristics: To determine the proportion of benign, borderline, and malignant PT in the Chinese population, as well as the distribution patterns of demographic and clinical features.

(2) Evaluate current treatment patterns: To depict the landscape and temporal trends of surgical procedures, margin status, lymph node surgery, and adjuvant radiotherapy/chemotherapy for PT in China over the past two decades.

(3) Quantify prognostic outcomes: To calculate local recurrence rates, distant metastasis rates, and tumor-specific mortality rates for the overall cohort and by histological grade, and to describe the patterns of PT outcomes.

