## **5. Study Design**

### **5.1 Overall Design**

[figure not shown]
This is a multicenter, retrospective cohort study. Data will be collected from patients who underwent breast surgery at the Departments of Breast Surgery of the following eight participating centers between January 1, 2001, and December 31, 2023:

- Sun Yat-sen Memorial Hospital, Sun Yat-sen University
- The First People's Hospital of Foshan
- Sun Yat-sen University Cancer Center
- Peking University Shenzhen Hospital
- Foshan Women and Children's Hospital
- The First Affiliated Hospital of Guangzhou Medical University
- Zhongshan People's Hospital
- Shanwei People's Hospital

The expected sample size is approximately 3,500 patients. Using real-world data over nearly 20 years, the study will systematically describe the clinicopathological characteristics, treatment patterns, and long-term prognosis of breast PT in China, and identify independent risk factors through descriptive analysis, propensity score methods, competing risk models, and sensitivity analyses.

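### The cohort is called national, but its eight tertiary hospitals appear to lie in one province, so its pooled grade proportions, treatment patterns and outcome rates cannot be presented as estimates for China

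*Combined protocol and SAP*

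**What the plan says.** **Claimed scope.** Section 1 (Abstract) states: "This is a national, multicenter, retrospective cohort study based on real-world data from approximately 3,500 patients". It describes the sites as "across 8 tertiary hospitals in China" and gives the intended use: "This study will provide Chinese population evidence to support personalized treatment and guideline updates". The primary objective in section 3.1.1 is to be met "using 20-year real-world data from a national multicenter cohort". Secondary objective (1) in section 3.1.2 reads: "To determine the proportion of benign, borderline, and malignant PT in the Chinese population". Secondary objective (2) and the closing paragraph of section 5.1 likewise refer to phyllodes tumour (PT) in China as a whole.

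**Actual source.** Section 5.1 states: "Data will be collected from patients who underwent breast surgery at the Departments of Breast Surgery of the following eight participating centers". Six of the eight names carry a city: Foshan twice, and Guangzhou, Shenzhen, Zhongshan and Shanwei once each. The other two are hospitals of one university and carry no city. The site called "Peking University Shenzhen Hospital" is a Shenzhen hospital despite the university in its name.

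**The plan's own standard.** Section 2.2.5 comments on an earlier Chinese dual-centre study of 829 cases. Among its reasons is "limited geographic representation, it still cannot fully capture the characteristics of the entire Chinese population". Section 2.2.2 says that the epidemiology of PT differs by region.

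**The concern.** The title-level description and two secondary objectives give the study a property that its site list does not show. If the plan is followed as written, the case mix and practice of eight tertiary hospitals would be reported as the grade distribution and treatment landscape of China, and the pooled recurrence, metastasis and survival rates as those of Chinese patients. Section 1 says the results are meant to inform guideline updates, so readers would be invited to use the figures in that sense. The plan holds an earlier study to a standard of geographic coverage and then does not apply that standard to itself.

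**Working it through.** **Step 1: claim against source.**

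| Element | Where | Content |
|---|---|---|
| Scope label | Sections 1 and 3.1.1 | National |
| Target of grade proportions | Section 3.1.2(1) | The Chinese population |
| Target of treatment patterns | Section 3.1.2(2) | China, about two decades |
| Hospital level | Section 1 | Eight of eight tertiary |
| Hospital location | Section 5.1, read from names | Foshan (2), Guangzhou, Shenzhen, Zhongshan, Shanwei; two names without a city |

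By general geography the two university hospitals are in Guangzhou, and all five cities are in Guangdong Province. The documents do not say so. What they do show is that no listed hospital is named for a city elsewhere in China.

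**Step 2: does anything in the plan connect the sample to the country?**

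- Section 5.3(3), consecutive enrolment: guards against selection within the eight centres only.
- Section 5.3(6), shared frailty or GEE: handles differences among these centres only.
- Section 5.4.1: the sample is every eligible patient at the eight centres, projected from their caseloads. There is no population sampling frame.
- Section 5.4.2(6): the sensitivity analyses include none by centre.
- No section plans weighting or standardisation to a wider population, comparison with other Chinese data, or a statement of limited generalisability.

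**Step 3: reproduce the plan's own figure.** Section 5.4.1 expects about 380 recurrences from 3,500 patients at about 11%, with a grade mix of 7:2:1.

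- Events = N × rate = 3,500 × 0.11 = 385.
- From the grade mix and the recurrence rates in section 2.1 (7.1%, 16.7%, 25.1%): 0.7 × 7.1 + 0.2 × 16.7 + 0.1 × 25.1 = 4.97 + 3.34 + 2.51 = 10.82%. Then 3,500 × 0.1082 = 378.7 events.

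Both agree with the stated figure, so the arithmetic is not at fault. The second line also shows that the overall rate is a weighted average in which the grade mix supplies the weights.

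**Step 4: how far the pooled rate moves with case mix (illustration).** Section 2.2.2 gives a benign share of 60% to 75%. Assume that the remainder splits 2:1 borderline to malignant, as in the planned mix, and that grade-specific rates stay fixed.

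- 60% benign: 0.600 × 7.1 + 0.267 × 16.7 + 0.133 × 25.1 = 4.26 + 4.45 + 3.35 = 12.06%, or 422 events per 3,500.
- 75% benign: 0.750 × 7.1 + 0.167 × 16.7 + 0.083 × 25.1 = 5.33 + 2.78 + 2.09 = 10.20%, or 357 events per 3,500.

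The gap of about 1.9 percentage points arises from case mix alone. It is not an estimate of bias in this cohort.

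**The case against.** Four arguments on the other side deserve weight.

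1. *The plan already reports by grade.* Sections 3.1.2(3) and 5.4.2(1) give event rates overall and by grade, and section 5.4.2(6) stratifies all primary analyses by grade. A reader can set the pooled figure aside or re-weight it. This stands, and it is why the point is confined to pooled, absolute quantities. It does not help the grade proportions themselves, nor does it remove regional practice or referral effects within a grade.
2. *Chinese population may simply mean Chinese patients.* Sections 2.1 and 2.2.5 contrast Chinese or Asian data with Western data, so the phrase need not imply a representative sample. That is a fair reading of the abstract's last sentence. It does not rescue the word national, or an objective to determine proportions in that population.
3. *The expected mix looks ordinary.* The 70% benign share expected at these centres lies inside the 60% to 75% of section 2.2.2. This stands as evidence against a marked skew. It does not make the sample national.
4. *The province is not in the documents.* This is correct, and the location is marked above as general geography. Without it, eight tertiary hospitals with no sampling frame still cannot by themselves yield population proportions.

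A reader might also infer that the cancer centre on the list draws higher-grade cases and skews the pooled results. No section says so, and singling out that centre for exclusion would rest on an assumption.

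**Conclusion.** The point holds as one of scope and external validity. The design does not have the national property claimed in sections 1 and 3.1.1, and it cannot deliver secondary objectives (1) and (2) as worded. It affects the pooled absolute quantities: grade proportions, treatment patterns and trends, and overall recurrence, metastasis and survival rates. No planned analysis fails because of it. Descriptive results for these centres remain valid, and prognostic associations within the cohort and grade-specific outcomes are much less affected. It would be wrong to conclude that the study cannot inform prognosis.

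The documents give no basis for sizing the bias. A reader might set the nominal precision of the malignant share against it: 1.96 × √(0.10 × 0.90 / 3,500) = 0.0099, about 1.0 percentage point. From that the reader might infer that selection error is several times larger. The half-width measures sampling error only and says nothing about the size of selection, so that inference has no support. The range of 12.1% to 10.2% shows only that a pooled rate depends on case mix; it rests on fixed grade-specific rates and the assumed 2:1 split.

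**What to change.** - In sections 1 and 3.1.1, replace the national label with a regional multicentre tertiary-hospital description. Name the province once the sponsor has confirmed the locations.
- Restate secondary objectives (1) and (2) in section 3.1.2, and the matching wording on China in section 5.1, as referring to PT patients operated on at the participating centres in the study period.
- Add a statement that generalisability beyond these centres is not established, and confine the conclusions to that population.
- In section 5.4.2(1), add a table of grade mix and pooled local recurrence, distant metastasis and overall survival by centre, with confidence intervals.

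The cost is a few wording changes and one table from data already collected. Centres average about 438 patients (3,500 / 8), so by-centre figures for the rarer events will be imprecise and should be read descriptively. The real price is a less ambitious title and conclusion.

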## 2. Background

### 2.1 Overview of Breast Phyllodes Tumor

Phyllodes tumor (PT) of the breast is a rare fibroepithelial neoplasm composed of both stromal and epithelial components, accounting for less than 1% of all breast tumors [1]. Clinically, it typically presents as a rapidly growing, painless mass. According to the World Health Organization (WHO), PT is classified into three grades based on histological features: benign, borderline, and malignant, with reported recurrence rates of 7.1%, 16.7%, and 25.1%, respectively [2]. The median/mean age at diagnosis ranges from 36.4 to 55 years, and the mean tumor size ranges from 3.7 to 11.3 cm. Malignant PT has the highest rate of distant metastasis, ranging from 6.5% to 62.5%, primarily via hematogenous spread, with the lungs and bones being the most common sites [3].

Because PT is rare, large-scale studies on its etiology, diagnosis, treatment, and prognosis are very limited. PT can grow very rapidly; delayed diagnosis and treatment may allow the tumor to become so large that surgery is no longer an option. Current imaging modalities (ultrasound, mammography, MRI) have limited ability to differentiate PT from other breast lesions and to accurately predict histological grade. Moreover, due to the often large tumor size and significant intratumoral heterogeneity, small needle biopsy samples may not fully represent the entire lesion, so accurate histological grading still relies on complete pathological evaluation of the excised tumor. PT is not sensitive to radiotherapy or chemotherapy; the mainstay of treatment is complete surgical excision [4]. The efficacy of adjuvant therapies such as targeted therapy and immunotherapy in PT requires further investigation. Although histological grade can, to some extent, predict patient outcomes, some benign PT may recur repeatedly or even undergo malignant transformation, whereas some malignant PT may remain stable for long periods. The current grading system does not fully explain individual differences in prognosis.

In recent years, most prediction models for PT have been built using Western population data from public databases such as SEER, with little validation in Asian populations. Most are single-center, small-sample retrospective case series, typically including dozens to a few hundred cases, lacking sufficient statistical power [4-9]. Many models have only been validated internally within the same database, without external, especially multicenter, validation, so their real-world predictive performance is

uncertain. Research content has mostly focused on clinical and imaging characteristics, differential diagnosis between benign and malignant PT, and comparisons of different surgical approaches on prognosis. Few studies have further analyzed postoperative recurrence and metastasis patterns. Larger sample sizes are still needed to explore risk factors for rare events such as multiple recurrences, distant metastasis, and death, and to reflect real-world clinical practice.

## **2.2 Current State of Research – Domestic and International**

### **2.2.1 Clinicopathological Features**

International research on breast PT began early. As early as 1774, this rare tumor was described as a "giant fibroadenoma" [10]. In 1838, Johannes Muller first used the term "cystosarcoma phyllodes" to describe PT, characterizing it as a sarcoma-like lesion with a cystic, leaf-like cut surface, rapid clinical growth, and large size. In 1981, the WHO adopted the term "phyllodes tumor" and defined it as "a rare fibroepithelial neoplasm with a leaf-like structure, composed of breast fibrous connective tissue and epithelial components" [11]. With deeper understanding of PT features, the 2019 WHO three-tier classification (benign, borderline, malignant based on tumor borders, stromal cellularity, stromal atypia, mitotic count, stromal overgrowth, and malignant heterologous elements) has become the internationally accepted diagnostic standard [12].

### **2.2.2 Epidemiology**

PT accounts for less than 1% of all breast tumors, and its epidemiological characteristics show distinct racial, regional, and age differences. As early as 1987, Chua et al. noted that PT incidence is higher in non-white populations, particularly in Asian women [13]. Asian PT patients are often younger (peak age 25-30 years), while Western patients are typically in their 40s. In 1993, Bernstein et al. reported that Latinas have a higher risk of PT compared to other racial groups. Age distribution varies by race, with Asian and Latina patients being significantly younger on average than non-Latina white patients [14]. Moten and Goldberg, in a large analysis of 1,202 patients with malignant PT from the SEER database, found that minority groups (Black, Hispanic, Asian) were diagnosed at significantly younger ages and had a higher risk of large tumors (>5 cm) and tumor extension beyond breast tissue [15].

Multiple studies show that the incidence of PT is approximately 2.1 per million women, accounting for 0.3%-1.0% of all breast tumors, with age at diagnosis concentrated between 35 and 55 years (median 45 years). Histologically, about 60%-75% of PT are benign, but both benign and malignant PT have the potential for local recurrence [3,5,6]. A systematic review and meta-analysis by Yu et al. of 52 real-world studies found an overall recurrence rate of approximately 12.6%, with risk increasing significantly with higher pathological grade: recurrence rates for benign, borderline, and malignant PT were approximately 7.1%, 16.7%, and 25.1%, respectively [10].

### **2.2.3 Treatment Patterns**

Surgical resection is the only curative treatment for PT. The basic principle is wide local excision, but the optimal margin width remains controversial. The NCCN guidelines recommend negative margins of  $\geq 1$  cm, but several recent studies have questioned this. Rosenberger et al. (2021), in a multicenter cohort of 550 cases, suggested that margin width requirements may be individualized, and that some borderline PT with margins

<1 cm may be safe [16]. A Swedish multicenter real-world study of 191 cases (1999-2018) found that, in multivariate analysis, margin status was not significantly associated with local recurrence or overall survival [17]. PT is not sensitive to radiotherapy or chemotherapy, and the efficacy of targeted therapy, immunotherapy, and other adjuvant treatments requires further study. Regarding lymph node management, meta-analyses and consensus suggest that axillary lymph node metastasis rates are <5%, so routine dissection is not recommended [10].

In 2025, the Breast Surgery Group of the Chinese Society of Surgery, Chinese Medical Association, published the "Clinical Practice Guidelines for the Diagnosis and Treatment of Breast Phyllodes Tumors (2025 Edition)" [18], marking the beginning of standardized diagnosis and treatment of PT in China. The guidelines provide recommendations on surgical margins, lymph node management, and adjuvant therapy based on available evidence, but the guideline developers also noted that due to the lack of high-quality Chinese population data, some recommendations are still mainly based on foreign studies.

#### **2.2.4 Prognostic Factors**

Domestic and international studies consistently agree that WHO histological grade (benign, borderline, malignant) is the most important prognostic factor. Higher grade is associated with greater risks of recurrence and metastasis. In addition, margin status, stromal overgrowth, tumor size, and patient age have also been identified as key factors affecting local recurrence [18-20]. Sun Yat-sen Memorial Hospital, Sun Yat-sen University, previously developed and validated a nomogram based on clinical and pathological factors from 334 PT cases using Cox regression to assist in evaluating PT prognosis, with external validation [21]. Benign PT does not significantly affect overall survival, so survival-related prognostic models mainly focus on borderline and malignant PT [9,22].

#### **2.2.5 Gaps in Current Research – Domestic and International**

Domestic research on PT started relatively late. Xu et al. (2022) noted that Chinese studies have focused on clinical presentation, pathological diagnosis, and surgical treatment, but sample sizes are generally small, making multivariable adjustment difficult [25]. Most published studies are single-center retrospective analyses of dozens to a few hundred cases, lacking large-scale, national multicenter studies. The largest Asian retrospective study to date, from the electronic database of the First Affiliated Hospital of Xi'an Jiaotong University (Li et al., 2025) [24], is a dual-center study of 829 cases, but due to the rarity of the disease and limited geographic representation, it still cannot fully capture the characteristics of the entire Chinese population.

Although international studies have relatively larger sample sizes, they are mostly based on Western populations, and Chinese patient data are lacking. Moreover, most are single-center retrospective analyses, and sample sizes are still insufficient for adequate subgroup analyses. Currently, there are few systematic studies on recurrence patterns (time to recurrence, number of recurrences, grade progression after recurrence), and the dynamic pattern of PT progression remains to be further elucidated.

### **3. Study Objectives and Endpoints**

#### **3.1 Objectives**

##### **3.1.1 Primary Objective**

To systematically elucidate the survival and prognostic characteristics of Chinese patients with breast phyllodes tumor (PT) using 20-year real-world data from a national multicenter cohort.

##### **3.1.2 Secondary Objectives**

(1) Describe distribution characteristics: To determine the proportion of benign, borderline, and malignant PT in the Chinese population, as well as the distribution patterns of demographic and clinical features.

(2) Evaluate current treatment patterns: To depict the landscape and temporal trends of surgical procedures, margin status, lymph node surgery, and adjuvant radiotherapy/chemotherapy for PT in China over the past two decades.

(3) Quantify prognostic outcomes: To calculate local recurrence rates, distant metastasis rates, and tumor-specific mortality rates for the overall cohort and by histological grade, and to describe the patterns of PT outcomes.

##### **3.1.3 Exploratory Objectives**

(1) Analyze recurrence event patterns: To analyze the time distribution of recurrences, number of recurrences, and probability of pathological grade progression after recurrence, providing clinical insights into tumor progression mechanisms.

(2) Identify independent prognostic factors: To screen independent risk factors for local recurrence, distant metastasis, and survival using multivariable regression methods, and to compare differences in prognostic factors across pathological grades, providing evidence for personalized follow-up and treatment decisions.

(3) Lay the foundation for prospective studies: The database generated from this study will provide hypotheses and a theoretical framework for future prospective, interventional clinical research.

